2.3.1 Minimisation criteria in randomisation algorithm

- Age
 - o < 70 versus \geq 70 years
- Index sICH location
 - o Only supratentorial lobar regions are affected; yes versus no
- Probability of a good outcome at six months (10)
 - o < 0.15 versus \geq 0.15
- Days from index sICH to randomisation
 - o 0 to 6 days versus 7 to 30 days versus > 30 days
- Antiplatelet drug the patient's physician would use if allocated (this criterion only applies to the antiplatelet trial)
 - o Aspirin only; yes versus no

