2.4 Sample size

The sample size estimation was made before the initiation of the study. A fourfold increase in the annual rate of recurrent sICH on antithrombotic drugs (from 2% to 8%) was considered unacceptable and higher than any plausible beneficial effect antithrombotic drugs would have on ischaemic events.

With power of 80% and a 5% significance level to detect an increase of the annual rate of recurrent sICH from 2% to 8% with antithrombotic therapy, the sample size was estimated to 500 participants randomised to intervention versus control. The sample size estimation was made for the trial as a whole, and not as two separate trials investigating the effect and safety of antiplatelets and effect and safety of anticoagulants as two separate trials. No sample size estimation for the two separate trials was performed. Regardless of this, analyses will be made for antiplatelet treatment versus control and anticoagulant treatment versus control separately.

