5.2 Analysis methods

Analyses will be performed separately for participants included in the antiplatelet trial and participants included in the anticoagulant trial.

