5.2.1 Primary analysis

Primary analysis is a comparison between groups of time-to-first event of new symptomatic sICH during two-year follow-up. This will be assessed by generating life tables, Kaplan-Meier curves and applying log-rank test.

The sample size calculation, performed before the study was started, is based on comparisons of proportions. However, in the protocol (latest protocol version v210421), time-to-event-analysis is defined as primary analysis. We will follow the protocol.

To adjust the differences between the groups, Cox proportional hazards (PH) regression model will be used. The results will be presented as an adjusted hazard ratio with the corresponding 95% CI.

All regression analyses will be adjusted for the variables being part of the minimisation criteria. If adjustment for all these variables is not possible due to few events (and consequently low power), age (< 70 versus \geq 70) and ICH location will be prioritized.

If the PH assumption is violated, time-dependent covariates will be included.

Since death is a competing risk, we will perform competing risk model as a sensitivity analysis.

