5.2.2. Secondary analyses

Secondary dichotomous composite outcomes will be analysed using the same statistical approach as primary outcome, i.e. by Kaplan-Meier curves, log-rank test, and Cox PH model. Ordinal outcome of function (modified Rankin Scale) will be analysed by an ordinal logistic regression model if the proportional odds assumption is confirmed. Adjustments for covariates will be performed in the same manner as for primary analysis.

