5.2.3 Exploratory analyses

If appropriate, primary and secondary outcomes will be compared between subgroups of patients defined by median age, timing of treatment initiation (0 to 6 days, 7 to 30 days and \geq 31 days) and haemorrhage location (lobar versus non-lobar). For participants randomised to anticoagulants versus control, relevant subgroups also include CHA²DS²VASc score (median score as cut-off) and HAS-BLED score (median score as cut-off). The same statistical analyses as described above will be applied.

If low power, we will only present descriptive numbers and not statistical tests.

5.2.4 Hierarchical structure:

Since the study is multicentre, data might exhibit a hierarchical structure with some degree of cluster effect within study centres. The intra-class correlation coefficient (ICC) will be estimated to assess the possible cluster effect in all outcome variables. If ICC will show to be non-negligible suitable adjustment of statistical methods specified above will be applied through inclusion of random effects on study centre into the considered models. In such a

case, frailty models (Cox PH model with fixed and random effects) and generalized linear mixed models will be estimated instead of Cox PH model and ordinal regression model, respectively.

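### Does the SAP need a numeric event threshold before it cuts back covariates or drops subgroup tests?

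*SAP*

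**What the plan says.** In SAP 5.2.1 the groups are compared on new symptomatic sICH over two years by life tables, Kaplan-Meier curves and the log-rank test. A Cox model is then added: "The results will be presented as an adjusted hazard ratio with the corresponding 95% CI". Its default covariates are all the minimisation factors of 2.3.1. One of them, aspirin only, is limited to one part ("this criterion only applies to the antiplatelet trial").

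The exception starts "If adjustment for all these variables is not possible due to few events (and consequently low power". It names age, split at 70, and location as the covariates to favour ("ICH location will be prioritized"). SAP 5.2.2 extends the rule to secondary outcomes: "Adjustments for covariates will be performed in the same manner as for primary analysis". For subgroups, SAP 5.2.3 says: "If low power, we will only present descriptive numbers and not statistical tests".

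Both rules work within a part, because "Analyses will be performed separately for participants included in the antiplatelet trial and participants included in the anticoagulant trial". SAP 2.4 adds: "No sample size estimation for the two separate trials was performed".

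**The concern.** The adjusted hazard ratio is the only effect estimate named for the primary outcome, since a log-rank test gives only a p-value. Whether its model has two covariates or all of them depends on full adjustment being impossible, and the SAP does not define impossible. It could mean that the fit fails to converge, or that there are too few events per parameter. With about 24 events in a part, a convergence reading would usually keep the full model. A rule of 5 events per parameter would keep only age and location, and a rule of 10 would reject even that.

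The trial is open (SAP 2.1), and the SAP does not say that the choice is made on events pooled over arms before allocation is revealed. If the models gave clearly different answers, the reported estimate could be chosen after the results were seen. The subgroup rule has the same gap. For the modified Rankin Scale, a condition about few events has no obvious meaning.

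**Working it through.** **The plan's own figure.** Neither rule has a number to reproduce. The only related figure is the total of 500 in SAP 2.4. For 2% versus 8%, two-sided 5% and 80% power:

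n per arm = [1.96·√(2·0.05·0.95) + 0.842·√(0.02·0.98 + 0.08·0.92)]² / 0.06² ≈ 206, or 412 in total.

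With a continuity correction it is 239 per arm, or 478. So 500 is somewhat conservative, and nothing below depends on it.

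**Expected events.** Two-year risks are 1 − 0.98² = 0.0396 and 1 − 0.92² = 0.1536, with mean 0.0966. The hazard ratio is ln 0.92 / ln 0.98 = 4.13. Part sizes of 250, 150 and 100 are assumptions.
- No effect (N × 0.0396): 9.9, 5.9, 4.0 events.
- Planned fourfold increase (N × 0.0966): 24.2, 14.5, 9.7 events.

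**Parameters, antiplatelet part.** Treatment 1, age 1, location 1, probability of good outcome 1, days 2 (three levels) and aspirin 1 make 7. The smaller model has 3. Events per parameter in the full model are 1.4, 0.85, 0.57 (no effect) or 3.5, 2.1, 1.4 (fourfold), so the exception may well come into play.

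**Does the choice move the treatment estimate?** I simulated 1,008 antiplatelet parts per scenario, with minimisation at probability 0.8 on the factors of SAP 2.3.1, exponential event times, two years and no deaths. Assumed prevalences: age 70 or over 70%, lobar 35%, low probability of good outcome 20%, days 15/30/55%, aspirin only 60%. Assumed hazard ratios: age 1.5, lobar 2, low probability 1.5, 0 to 6 days 1.5. A coefficient counts as not finite if its absolute value reaches 8. Failure rates are among trials with events in both arms.

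| Scenario, part size | Any coefficient not finite, full | Treatment not finite, full | Treatment not finite, age + location | HR ratio, full vs smaller: median (90th percentile) |
|---|---|---|---|---|
| No effect, 250 | 33% | 0.1% | 0% | 1.04 (1.16) |
| No effect, 150 | 64% | 0.7% | 0% | 1.09 (1.42) |
| No effect, 100 | 81% | 4.6% | 0% | 1.16 (1.73) |
| Fourfold, 250 | 1% | 0% | 0% | 1.03 (1.09) |
| Fourfold, 150 | 10% | 0% | 0% | 1.05 (1.19) |
| Fourfold, 100 | 29% | 0% | 0% | 1.09 (1.48) |

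Smaller runs of the same set-up (300 to 400 trials) gave 1.7% to 12% for the 4.6% cell, so read it as that range. Nearly all failures lie in nuisance covariates. The treatment coefficient is almost always estimable, and in the named fallback it always was here.

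**Compared with sampling error.** Take SE(log HR) ≈ √(1/e₀ + 1/e₁), where e₀ and e₁ are the expected events per arm. The confidence limit lies a factor exp(1.96·SE) from the estimate.
- No effect: e₀ = e₁ = 4.95, 2.97, 1.98. SE = 0.64, 0.82, 1.01. Factor 3.5, 5.0, 7.2.
- Fourfold: e₀ as above, e₁ = 19.2, 11.5, 7.7. SE = 0.50, 0.65, 0.80. Factor 2.7, 3.6, 4.8.

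Even the 90th percentile of the shift is well inside these factors.

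**Subgroups.** With 24 events split 12/12, the SE of the log ratio of hazard ratios is √(4/12 + 4/12) = 0.816. The ratio detectable with 80% power is exp(2.80 × 0.816) = 9.8. With 10 events split 5/5 it is about 35. Any sensible cut-off calls this low power.

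**The case for a change.** The strongest reply is that favouring two covariates does not exclude the others. Age and location plus any subset of the remaining three factors gives 2³ = 8 models in the antiplatelet part and 2² = 4 in the anticoagulant part. Over the eight, the largest hazard ratio exceeds the smallest by a median (90th percentile) of 1.07 (1.21), 1.16 (1.56), 1.33 (2.69) at 250, 150, 100 with no effect, and 1.04 (1.11), 1.08 (1.24), 1.15 (1.48) with the fourfold effect (2,000 trials per scenario). For a safety outcome the worry is a lost signal, and under the fourfold effect the eight models disagree on p < 0.05 in 3%, 8% and 11% of trials. There is also no stated step if an arm has no event, which occurred in 0.8%, 9% and 25% of trials with no effect. Recruitment was slow (SAP 2.5), so small parts cannot be ruled out.

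The arithmetic stands, and so does the gap in wording. Its reach is limited:
- The ordinary reading is two models, the full set and age plus location. The range over eight takes extremes that an analyst following the text would not search for.
- Searching would not create false positives: at least one of the eight models gives p < 0.05 in 2.9%, 1.0% and 0.7% of trials with no effect.
- A signal cannot be lost from the log-rank result, which uses no covariates.
- If an arm has no event, no ordinary Cox model gives a finite hazard ratio whatever its covariates. The planned life tables, Kaplan-Meier curves and log-rank test still report the result.
- On the modified Rankin Scale, a condition about few events that does not apply leaves the full set in force.
- The subgroup rule sits under exploratory analyses and can only reduce testing.

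The available replacements gain little. Making age plus location the main model would reverse a defensible choice to adjust for all minimisation factors. A penalised model mainly treats nuisance coefficients. Any events-per-parameter cut-off is a convention: 5 per parameter would need 35 events for the full antiplatelet model, more than the 24 expected in a part of 250 even under the fourfold increase.

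**Conclusion.** No change is called for. The SAP leaves a threshold unwritten, but it gives a default model, a reason to leave it and the covariates to keep. An analyst would sensibly fall back to treatment, age and location when the full model fits poorly, and would report doing so. Only the adjusted hazard ratio and its interval are affected. Between the two natural models the median shift is 3% to 4% at a part size of 250 and 9% to 16% at 100. It can be larger in single trials at 100 to 150, where the interval is already very wide. The log-rank p-value does not move. These sizes rest on assumed part sizes, covariate mix and covariate effects, because the SAP states none. A sentence giving the criterion would be harmless tidying, but the conclusions do not depend on it.

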5.2.2. Secondary analyses

Secondary dichotomous composite outcomes will be analysed using the same statistical approach as primary outcome, i.e. by Kaplan-Meier curves, log-rank test, and Cox PH model. Ordinal outcome of function (modified Rankin Scale) will be analysed by an ordinal logistic regression model if the proportional odds assumption is confirmed. Adjustments for covariates will be performed in the same manner as for primary analysis.

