4.4 Baseline patient characteristics

4.4.1 Baselines variables

The following baseline variables will be reported: Age, sex, comorbidities, living arrangements, functional status at randomisation, medications used before randomisation, physiological parameters, time from sICH to randomisation, location (non-lobar versus lobar) and volume (< 30 ml versus \geq 30 ml) of sICH on CT or MRI before randomisation.

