5.1 Outcome definitions

5.1.1. Primary outcome:

The primary outcome is new symptomatic sICH (fatal or non-fatal) found on CT scan, MRI scan or by autopsy over at least two years follow-up. We will perform analysis of time to first event after two years follow-up as primary analysis and after total follow-up time as

secondary analysis. Those not experiencing the event will be censored at last available follow-up, death unrelated to a primary outcome or voluntary withdrawal from the trial (whichever occurs soonest).

5.1.2. Secondary outcomes:

Secondary outcomes will be analysed as composite endpoints except for functional outcome at two years (according to modified Rankin Scale) and death of any cause. The secondary endpoints will also be reported individually. Secondary outcomes will be analysed as reported by investigator.

5.1.2.1 Composite secondary outcomes:

The following composite endpoints will be analysed:

- **Major ischaemic events:** Ischaemic stroke, myocardial infarction, mesenteric ischaemia, peripheral arterial occlusion, deep vein thrombosis, pulmonary embolism, revascularisation procedures (carotid, coronary or peripheral)
- **Major haemorrhagic events:** symptomatic intracerebral haemorrhage, other symptomatic intracranial haemorrhages (epidural, subdural or subarachnoid haemorrhages both spontaneous and traumatic), symptomatic major extracranial haemorrhage requiring transfusion with more than 2 units of whole blood or red cells, a fall in > 2.0 g/L haemoglobin, bleeding in a critical area or organ (intraspinal, intraocular, retroperitoneal, intra-articular or pericardial, or intramuscular with compartment syndrome) or haemorrhage leading to death.
- **Major adverse cardiovascular events (MACE)** defined as ischaemic stroke, myocardial infarction, other major ischaemic events, intracerebral haemorrhage, other intracranial haemorrhage, major extracranial haemorrhage or vascular death.

Time to event for secondary outcomes except for functional outcome according to modified Rankin Scale will be defined in the same way as for primary outcome. Modified Rankin Scale is not subject to survival analysis and thus time to event is irrelevant for this outcome.

As for the primary outcome, secondary outcomes will be analysed as time to first event after two-years follow-up and after total follow-up time.

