5.3 Missing data

During the study period, comprehensive efforts will be made to obtain complete outcome data. In case of missing values, different approaches will be considered to handle them, such as complete case analysis, multiple imputation or inverse probability weighting. Thorough sensitivity analyses will be performed in the case of imputation.

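### The ordinal model for two-year modified Rankin Scale omits functional status at randomisation, a baseline variable the plan already reports, and so gives up some power

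*SAP*

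**What the plan says.** Section 5.2.2 analyses mRS at two years by ordinal logistic regression, provided proportional odds is confirmed. Its covariates are set by reference: "Adjustments for covariates will be performed in the same manner as for primary analysis". Section 5.2.1 then states: "All regression analyses will be adjusted for the variables being part of the minimisation criteria". Section 2.3.1 lists those variables:

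- age below 70 or not;
- index bleed confined to lobar regions or not;
- "Probability of a good outcome at six months", split at 0.15;
- days from bleed to randomisation, in three groups;
- aspirin only or not, in the antiplatelet part.

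Section 4.4.1 includes "functional status at randomisation" among the baseline variables to be reported. No model in section 5.2 uses it. The centre random effect allowed by 5.2.4 would not supply it.

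Two other provisions matter. Section 5.2.1 has a fallback to age and location, opening "If adjustment for all these variables is not possible due to few events". Section 5.3 leaves the handling of missing values open, "such as complete case analysis, multiple imputation or inverse probability weighting".

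**The concern.** A covariate rule written for a Cox model with possibly few events is carried over to an ordinal scale. For that outcome, function at entry is an obvious candidate predictor. The only function-related term in the planned model is a two-level split of a predicted probability.

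In a proportional-odds model, leaving out a prognostic covariate pulls the odds ratio towards 1 and lowers power. Power is likely to be limited already: 5.2 analyses the two parts separately, and 2.4 says neither was sized on its own. Nothing here biases the planned test or touches the primary outcome.

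The fallback in 5.2.1 is most naturally read as not reaching mRS, since 5.1.2 says "Modified Rankin Scale is not subject to survival analysis". No gain is claimed from that point. The cross-reference could be read otherwise, so one clarifying sentence is worthwhile.

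**Working it through.** **The plan's own figure.** The SAP gives no power or sample size for mRS. Its 500 participants (2.4) are for recurrent bleeding and have no bearing on this model. The figure is used only to assume 250 per part, by an equal split.

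**Inputs from the SAP.** The minimisation factors (2.3.1), allocation by minimisation with probability 0.8 (2.3), two-sided testing at 5% (3.2), and the proportional-odds model (5.2.2).

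**Assumed inputs.**
- Partial correlation r between baseline function and two-year mRS, given the minimisation factors: 0.20 to 0.60.
- mRS shares 6/14/18/20/14/6/22%; six-level baseline function 8/17/20/20/25/10%.
- 25% below the 0.15 split, 65% aged 70 or over, 40% lobar, day groups 15/35/50%, 70% aspirin only.
- A treatment effect giving the planned model about 64% power (log odds ratio about 0.53).

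**Models compared by simulation** (10,000 runs per r at 250 participants). A is treatment plus all minimisation factors. B is A plus baseline function as one linear term.

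Effective-sample ratio = (mean z under B ÷ mean z under A)². Rough check: 1/(1 − r²).

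| r | A: log OR (SE) | B: log OR (SE) | Ratio | 1/(1 − r²) | Power, A to B |
|---|---|---|---|---|---|
| 0.20 | 0.527 (0.227) | 0.540 (0.228) | 1.04 | 1.04 | 64% to 65% |
| 0.30 | 0.525 (0.227) | 0.557 (0.229) | 1.11 | 1.10 | 64% to 68% |
| 0.40 | 0.527 (0.227) | 0.588 (0.231) | 1.21 | 1.19 | 64% to 72% |
| 0.60 | 0.533 (0.228) | 0.702 (0.236) | 1.62 | 1.56 | 65% to 84% |

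Worked line, r = 0.40: 0.527/0.227 = 2.32 and 0.588/0.231 = 2.55, so the squared ratio is about 1.20 (1.21 from the mean z values). Power is roughly Φ(z − 1.96): Φ(0.36) = 64% and Φ(0.59) = 72%. The Monte Carlo SE is 0.5 points per power. At 150 per part the ratios are 1.04, 1.11, 1.20 and 1.61. Type I error was 5.0–5.1% for A and 5.1–5.2% for B.

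**Missing baseline values** (completely at random), ratio against model A on everyone. Complete case costs roughly the missing fraction; for example, 1.11 × 0.90 = 1.00.

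| r | 10% missing: complete case | 10%: filled | 20% missing: complete case | 20%: filled |
|---|---|---|---|---|
| 0.20 | 0.94 | 1.04 | 0.84 | 1.03 |
| 0.30 | 1.00 | 1.10 | 0.89 | 1.08 |
| 0.40 | 1.09 | 1.19 | 0.97 | 1.16 |
| 0.60 | 1.47 | 1.54 | 1.31 | 1.45 |

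Filled means one value common to both arms; type I error with filling was 5.1–5.2%.

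**Sensitivity.** If r rises from 0.15–0.19 at 0–6 days to 0.44–0.50 after 30 days, one pooled linear term gives 1.11–1.22. For step or curved relations (r 0.36–0.40), the linear term gives 1.18–1.22 and category indicators 1.22–1.25, so the coding matters little.

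**Second simulation**, with simple balanced allocation and other assumed distributions, at 150, 250 and 500 participants and indexed by the Spearman correlation with mRS:
- about 0.04 (no independent effect): no gain;
- about 0.32: 71–72% to 74–77% power, ratio 1.09–1.11;
- about 0.54: 62–63% to 76–78% power, ratio about 1.4.

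Type I error was the same for both models (5.5–5.7%).

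**The case against.** Adjusting for the minimisation factors is standard and pre-specified, and those factors already carry prognosis, age, location and timing. Section 5.2.1 does not say whether the predicted probability enters as the split or as a continuous value. If continuous, less is left for baseline function to explain. What that score contains is not shown in the SAP, so its overlap with functional status is unknown.

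The size rests on assumptions throughout, and power near 64% is where extra information shows most. If planned power were 20%, z = 1.96 − 0.84 = 1.12; multiplying by √1.11 or √1.21 gives only about 22% or 23%. The variable's scale and completeness are not visible. The trial is open and follow-up was due to end in August 2024, so a late covariate change needs evidence that outcomes by arm were unseen. The protocol, not shown, may fix the covariate set.

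All of this stands as a limit on the size and on how the change is made. None of it removes the point: these arguments shrink the gain within the range given, and a gain near zero remains possible if baseline function adds little beyond the prognosis term.

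**Conclusion.** The point holds as a modest one. The mRS model uses only the minimisation factors, and a baseline variable already due to be reported is left unused. If its partial correlation with two-year mRS is 0.3–0.4, the loss is equivalent to 11–21% of the effective sample, or about 4 to 8 power points at the assumed 250 per part and 64% planned power. Near 0.2 it is about one point. This is lost efficiency on a secondary outcome. It is not bias, and the primary analysis is unaffected. The gain also depends on not dropping participants whose baseline value is missing, so the covariate and its missing-value rule must be fixed together. The change is recommended but not essential to validity.

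**What to change.** Add to 5.2.2:

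> The ordinal model for mRS at two years is adjusted for functional status at randomisation in addition to the minimisation factors. It enters as one linear term if it is recorded on an ordered scale, otherwise as indicators of its recorded categories. The few-events reduction in 5.2.1 applies to event outcomes only. The odds ratio is reported as conditional on these covariates.

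Add to 5.3:

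> Missing values of functional status at randomisation are filled with one value (the mean, or the most frequent category) computed over all participants of that part without regard to allocation, so that no participant is dropped from the mRS model for this reason. The approaches above apply to other missing values.

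If proportional odds is not confirmed, carry the same covariate into whichever model replaces the ordinal one.

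The cost is six sentences, dated, with a statement that outcome data by arm had not been seen. The model gains one parameter (five if six categories are used), and the odds ratio becomes conditional on baseline function. If the protocol fixes the covariate set, record this as an SAP change.
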